#### 11.4 Vital Signs

The on-treatment period will be defined as the time from the first dose of study drug until the date of the last oral study medication plus 28 days or date of last IV dose plus 5 months (ie, 152 days), whichever is the latest date. Vital sign measurements collected during the ontreatment period will be included in the summary tables. The vital sign measurements collected after the on-treatment period will only be presented in the data listings.

For visit-based summaries, vital signs evaluated during the actual scheduled cycle visit will be used, otherwise, any unscheduled vital signs evaluations that are closest and within the same actual scheduled cycle will be used. The data sets should highlight the value for the patient that went into the summary table, wherever feasible. The summary tables and graphs will only display data if the number of observations is greater than 10 in each treatment arm.

The summary of vital sign data will include descriptive statistics of the maximum, minimum and last value during the on-treatment period. Summaries using descriptive statistics of the change from baseline to the maximum, minimum, and last value during the on-treatment period will also be given.

#### 11.5 ECG

Local reads of ECG were collected at screening and end of study.

The QT interval was corrected by using both Fridericia's (QTcF) and Bazett's (QTcB) formula. The QTcF and QTcB intervals will be stratified into categories indicative of potential clinical significance. Each patient's maximum QTc intervals from baseline to end of treatment visits will be classified into the following: ≤450 msec, >450 to ≤480 msec, >480 to ≤500 msec, and >500 msec. For each patient's maximum change from the pretreatment ECG visit for QT and QTc, intervals will be classified into <30 msec, ≥30 to <60 msec, and ≥60 msec. Patients will also be classified according to the CTCAE grade 3 criteria of at least 2 on treatment QTc values >500 ms. The number and percentage of patients in each classified category will be presented.

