7.5.4.3 Vital Signs

Vital signs will include blood pressure, pulse, and body temperature and will be taken after the patient has been resting for at least 5 minutes during screening, at study visits during the Treatment Phase, and at the Treatment Discontinuation Visit.

7.5.4.4 12-Lead Electrocardiogram

For all patients, local 12-lead ECGs will be taken at screening (within 28 days prior to first dose of study drug), at End-of-Treatment Visit, and at both SFU1 and SFU2.

The following will be measured or calculated: heart rate, PR, QRS, QT, QTc, and rhythm. The investigator or qualified designee will review the ECGs locally and assess the results as normal or abnormal (clinically significant or not clinically significant).

If it is clinically indicated, ECGs can be performed at other times during the study.

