#### 11 SAFETY ANALYSIS

Safety and tolerability is one of the secondary study objectives. Overall safety and tolerability will be measured by the incidence of adverse events, serious adverse events, adverse events leading to discontinuation, deaths, specific laboratory abnormalities (worst grade) and changes from baseline.

The safety analyses will be presented for the safety population presenting the data for each treatment group separately (Arm A [rucaparib and nivolumab], Arm B [rucaparib], Arm C [nivolumab], and Arm D [placebo]). The analyses will be presented by the actual treatment given. Patients randomized to either treatment group containing IV Nivolumab (ie, Arm A or Arm C) who never receive Nivolumab, will be analyzed in the analogous treatment group containing IV Placebo (ie, Arm B or Arm D, respectively).

Summary tables are based on data that are found to be "on-treatment"/ "treatment-emergent" for the oral or IV study drug as outlined in the below sections.

All safety data which is considered treatment-emergent will be summarized. Treatment-emergent is defined as safety data with an onset date on or after the date of first dose of study medication until the date of last dose of oral study drug plus 28 days or date of last IV dose plus 5 months (ie, 152 days), whichever is the latest date.

Descriptive statistics of safety will be presented using the NCI CTCAE v5.0. All AEs, drug-related adverse events, serious adverse events (SAEs) and drug-related SAEs will be tabulated using the worst grade per NCI CTCAE v5.0 by system organ class and preferred term. On-study lab parameters including hematology, coagulation, chemistry, liver function, thyroid, adrenal and renal function will be summarized using worse grade by NCI CTCAE v5.0.

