#### 11.4 ECG

Local reads of ECG were collected at Screening and End of Study. Summaries using descriptive statistics of the observed value and change from baseline to end of study will also be given.

The QT interval was corrected by using both Fridericia's (QTcF) and Bazett's (QTcB) formula. Each patient's maximum QTc intervals will be classified according to the CTCAE V5 grades to the following categories: < 450 msec (Normal),  $\geq$  450 to  $\leq$  480 msec (Grade 1),  $\geq$  480 to  $\leq$  500 msec (Grade 2), and  $\geq$  500 msec (Grade 3). In addition, each patient's maximum change from baseline for QTc intervals will be classified into  $\leq$  30 msec,  $\geq$  30 to  $\leq$  60 msec, and  $\geq$  60 msec (Grade 3). The number and percentage of patients in each classified category will be presented.

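### ATHENA-COMBO SAP 11.5 lets a pre-treatment ECG set a patient's maximum-QTc category, misstates when ECGs are taken, and uses a Grade 3 QTc rule that differs from the ATHENA-MONO SAP

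*SAP*

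**What the plan says.** COMBO SAP 11.5 makes four statements.

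- Collection: "Local reads of ECG were collected at screening and end of study".
- Absolute bands: "Each patient's maximum QTc intervals from baseline to end of treatment visits will be classified into the following". The bands are ≤450, >450 to ≤480, >480 to ≤500 and >500 ms.
- Change bands: based on each patient's "maximum change from the pretreatment ECG visit for QT and QTc", in bands <30, ≥30 to <60 and ≥60 ms. No toxicity grade is attached.
- Grade 3: "Patients will also be classified according to the CTCAE grade 3 criteria of at least 2 on treatment QTc values >500 ms".

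COMBO SAP 11 defines on-treatment data as running from first dose to the later of "last dose of oral study drug plus 28 days or date of last IV dose plus 5 months (ie, 152 days".

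Protocol 7.5.4.4 schedules 12-lead ECGs at screening, "at End-of-Treatment Visit, and at both SFU1 and SFU2", and adds: "If it is clinically indicated, ECGs can be performed at other times during the study". Table 5 and its ECG footnote agree. Protocol 3.1.3 fixes no ECG at a routine dosing-cycle visit; there it is done only when clinically indicated.

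MONO SAP 11.4 covers the same trial and shares Arm B. It states: "Each patient's maximum QTc intervals will be classified according to the CTCAE V5" grades. It has no two-value requirement, and it labels its top change band (60 ms) Grade 3 as well.

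**The concern.** A table of maximum QTc in a safety section is read as what happened after dosing began. If the baseline ECG is eligible to be the maximum, the table partly describes the patients at entry. If SFU1 and SFU2 are left out, it also misses readings that the SAP itself counts as on treatment.

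The Grade 3 line raises a separate problem. It needs two qualifying readings, in a section that describes only one post-baseline ECG, and it does not name the visits that count. Two programmers could produce different tables from it. A reader who compares the MONO and COMBO reports could also find two Grade 3 QTc counts for Arm B with nothing to explain the difference.

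**Working it through.** The documents give no QTc rate or expected count, so there is no planned figure to reproduce. The check is a count of visits and a side-by-side reading.

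**1. What enters the maximum.** Scheduled ECGs under the protocol are screening (pre-treatment), EoT, SFU1 and SFU2. Read literally, the 11.5 span takes screening and EoT: two scheduled ECGs, one of them pre-treatment. It uses one of the three scheduled post-baseline ECGs. (If IV drug stops early and oral drug continues, SFU2 can come before EoT by date. Whether it then counts is not stated.)

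Example: 490 ms at screening, 440 ms at EoT.
- Maximum as written: max(490, 440) = 490, band >480 to ≤500.
- Post-baseline maximum: 440, band ≤450.
- Change: 440 − 490 = −50 ms, band <30.

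The absolute band moves by two categories and the change band is unaffected. Even if baseline were included in the change calculation, its own change is 0, which falls in the lowest band.

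**2. Neighbouring sections.** COMBO SAP 11.3 (laboratory) and 11.4 (vital signs) take maxima over the on-treatment period. Section 11.5 departs from this without giving a reason.

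**3. Scheduled post-baseline ECGs inside the on-treatment window.** Window end = max(last oral dose + 28 days, last IV dose + 152 days). SFU1 is 28 ± 7 days after the later last dose. SFU2 is about 152 ± 7 days after the last IV dose. EoT is taken to fall on the last dosing day. The dosing days are illustrative.

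| Pattern | Window end (day) | EoT | SFU1 | SFU2 | ECGs in window |
|---|---|---|---|---|---|
| Last IV 700, last oral 728 | max(756, 852) = 852 | 728 | 749–763 | 845–859 | 3, or 2 if SFU2 is after day 852 |
| Last IV 100, last oral 728 | max(756, 252) = 756 | 728 | 749–763 | 245–259, during oral dosing | 3, or 2 if SFU1 is after day 756 |
| IV never given, last oral 20 | 48 | 20 | 41–55 | none | 2, or 1 if SFU1 is after day 48 |

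So the protocol schedule usually supplies two or three ECGs in the window. On 11.5's own description (screening and end of study) there is one, and the two-value rule then needs an unscheduled ECG.

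**4. When the second reading falls.** If both drugs stop together, the first scheduled post-baseline ECG is EoT and the second is SFU1, nominally 28 days after the last dose (21 at the early edge of the visit window). Protocol 1.1.1.2.1 gives a rucaparib half-life of 11 to 29.8 h, so 28 × 24 / 29.8 = 22.6 to 28 × 24 / 11 = 61.1 half-lives have passed. Protocol 1.1.2.3.1 gives nivolumab 25 days, so 28 / 25 = 1.1 half-lives have passed.

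**5. The two SAPs on one Arm B patient.** Take 520 ms at EoT and normal QTc at SFU1 and SFU2, with no other ECG above 500 ms.
- MONO SAP 11.4: the single maximum is 520, so Grade 3.
- COMBO SAP 11.5: counted in the >500 ms band, but only one value exceeds 500, so not Grade 3 under the two-value rule.

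**The case against.** The best case for leaving the section alone has five parts.

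- **The signal is reported anyway.** Section 11.5 bands a single maximum, with its own >500 ms row, and has a ≥60 ms change row. The two-value rule is an addition. This stands: a single value above 500 ms up to EoT is labelled differently from MONO, but it is not lost.
- **Section 11 already limits summary tables to on-treatment data**, so the baseline wording may be loose drafting. This is possible, but the specific sentence says otherwise, and a programmer would follow it.
- **The two-value rule is attainable.** A reader might infer that no ECG is scheduled on treatment and that the rule cannot be met. The documents do not support that. The window usually holds two or three scheduled ECGs, SFU2 may be done at a cycle visit while oral drug continues, and unscheduled ECGs are allowed.
- **The half-life argument is one-sided.** SFU1 is long after rucaparib washout but only about one nivolumab half-life after a last infusion given at the same time. The window is meant to cover both drugs. This stands, so SFU1 cannot be called off-treatment for the combination.
- **MONO is not a clean model.** Section 11.4 carries the same collection sentence and does not say that its maximum is post-baseline. It also uses an oral-only window, so Arm B counts could differ for that reason too. Which SAP states the CTCAE criterion correctly depends on a source outside these documents. This stands, so the remedy is to reconcile the two SAPs rather than copy MONO.

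**Conclusion.** The point holds as a minor one. As written, the absolute QTc bands can be set by a pre-treatment ECG and leave out follow-up ECGs that the SAP's own window usually includes. The collection sentence does not match the protocol. The Grade 3 rule conflicts with the section's own account of what was collected, and it differs from the rule applied to the same Arm B in MONO. The change bands are not affected.

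How many patients would change category cannot be stated, because the documents give no QTc data. A reader might infer that the two-value count will be near zero by design, or that a zero would be an artefact. That is not shown. As an illustration, assume 400 patients and a 1% chance per ECG of exceeding 500 ms:

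- Independent readings, two ECGs: 400 × 0.01² = 0.04 patients.
- Independent readings, three ECGs: 400 × (3 × 0.01² × 0.99 + 0.01³) = 0.12 patients.
- Readings perfectly correlated within a patient: 400 × 0.01 = 4.0 patients, the same as a one-value rule on one ECG.

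The answer depends on a rate and a correlation that the documents do not give.

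The visit counts assume that patients attend follow-up within the protocol windows and that EoT falls at the last dose. No primary or key secondary endpoint is touched; this is a descriptive safety table.

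**What to change.** In COMBO SAP 11.5:

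1. Take the maximum QTc and the maximum change over post-baseline ECGs in the section 11 on-treatment window: EoT, SFU1 and SFU2 when they fall inside it, and unscheduled ECGs. Tabulate baseline separately or as a shift table.
2. Reconcile the Grade 3 QTc definition with MONO SAP 11.4, including whether the 60 ms change band carries a grade. The MONO primary analysis has already been run (data cut-off 23 March 2022), so in practice this means a change or an explained difference in the COMBO SAP. Show the single-value post-baseline >500 ms count beside any two-value count, and name the ECGs that count as on treatment.
3. Correct the collection sentence to screening, EoT, SFU1, SFU2 and clinically indicated ECGs.

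The cost is SAP wording and a table shell. No new ECGs or data are needed. A single-value count cannot be lower than a two-value count on the same ECGs, so the Grade 3 line may look less favourable.

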#### 11.6 Examination of Safety in Subgroups

Safety will be further explored in the following subgroups:

- Age groups ( $< 65, 65-74, \ge 75$ )
- Race (white, non-White)

For treatment comparison of Arm A (nivolumab + rucaparib) vs Arm B (rucaparib monotherapy) key safety analyses may also be summarized for specific molecular analysis populations (eg, by PD-L1 or HRD/tBRCA status).

Safety may be further explored by specific countries (eg, Japan, South Korea) for registration requirements, if needed.

Confidential 43 of 52

# 11.7 Japanese Open-label

The safety data from the Japanese Open–label cohort evaluating the combination of rucaparib and nivolumab will be summarized with standard demographics and safety tables.

Confidential 44 of 52

# **APPENDIX A: FACT-O (VERSION 4)**

Below is a list of statements that other people with your illness have said are important. Please circle or mark one number per line to indicate your response as it applies to the past 7 days.

**Physical Well-being** 

	y steat vven seing					
		Not at all	A little bit	Some- what	Quite a bit	Very much
1	I have a lack of energy	0	1	2	3	4
2	I have nausea	0	1	2	3	4
3	Because of my physical condition, I have trouble meeting the needs of my family	0	1	2	3	4
4	I have pain	0	1	2	3	4
5	I am bothered by side effects of treatment	0	1	2	3	4
6	I feel ill	0	1	2	3	4
7	I am forced to spend time in bed	0	1	2	3	4

Social/Family Well-being

		Not at all	A little bit	Some- what	Quite a bit	Very much
1	I feel close to my friends	0	1	2	3	4
2	I get emotional support from my family	0	1	2	3	4
3	I get support from my friends	0	1	2	3	4
4	My family has accepted my illness	0	1	2	3	4
5	I am satisfied with family communication about my illness	0	1	2	3	4
6	I feel close to my partner (or the person why is my main support)	0	1	2	3	4
Q	Regardless of your current level of sexual activity, please answer the following question. If you prefer not to answer it, please mark this box $\square$ and go to the next section.					
7	I am satisfied with my sex life	0	1	2	3	4

Confidential 46 of 52

# Please circle or mark one number per line to indicate your response as it applies to the past 7 days.

**Emotional Well-being** 

	8					
		Not at all	A little bit	Some- what	Quite a bit	Very much
1	I feel sad	0	1	2	3	4
2	I am satisfied with how I am coping with my illness	0	1	2	3	4
3	I am losing hope in the fight against my illness	0	1	2	3	4
4	I feel nervous	0	1	2	3	4
5	I worry about dying	0	1	2	3	4
6	I worry my condition will get worse	0	1	2	3	4

**Functional Well-being** 

	V	Not at all	A little bit	Some- what	Quite a bit	Very much
1	I am able to work (include work from home)	0	1	2	3	4
2	My work (include work from home) is fulfilling	0	1	2	3	4
3	I am able to enjoy life	0	1	2	3	4
4	I have accepted my illness	0	1	2	3	4
5	I am sleeping well	0	1	2	3	4
6	I enjoy the things I usually do for fun	0	1	2	3	4
7	I am content with the quality of life right now	0	1	2	3	4

Confidential 47 of 52

# Please circle or mark one number per line to indicate your response as it applies to the past 7 days.

## **Additional Concerns**

		Not at all	A little bit	Some- what	Quite a bit	Very much
1	I have swelling in my stomach area	0	1	2	3	4
2	I am losing weight	0	1	2	3	4
3	I have control of my bowls	0	1	2	3	4
4	I have been vomiting	0	1	2	3	4
5	I am bothered by hair loss	0	1	2	3	4
6	I have a good appetite	0	1	2	3	4
7	I like the appearance of my body	0	1	2	3	4
8	I am able to get around by myself	0	1	2	3	4
9	I am able to feel like a woman	0	1	2	3	4
10	I have cramps in my stomach area	0	1	2	3	4
11	I am interested in sex	0	1	2	3	4
12	I am concerned about my ability to have children.	0	1	2	3	4

Confidential 48 of 52

#### **Grading of Central and Local Laboratory Data**

The central laboratory provides CTCAE grades according to their lab Tox Grade Report. However, in some instances the Report indicates grading is derived without the use of a baseline result where v5.0 requires use of upper limit of normal (ULN) for normal baseline and increments above baseline for abnormal baseline. Therefore, the CTCAE grading criteria will be applied in a consistent manner across all laboratory assessment using stacked data that includes both central and local results.

#### **Normal Reference Ranges**

A reference range is a set of values that includes upper and lower limits based on a group of otherwise healthy people. The values may depend on age, gender, and specimen type and can also be influenced by circumstantial situations such as fasting and exercise.

Normal reference ranges for central laboratory assessments are contained within the data provided by the central laboratory. Each of the local laboratories provided normal ranges specific to the lab in which the test was done. These local ranges were entered into EDC and applied to results via the lab admin tool.

#### **Liver Function Tests**

Baseline results for four LTFs (ALT, AST, ALP and bilirubin) will not receive a numeric grade (grade 1-5). They will be categorized in relation to the ULN (eg, <=ULN, >ULN-3xULN, >3xULN-5xULN). Shifts in grade from baseline to maximum on-treatment post-baseline for these events (alanine aminotransferase increased, alkaline phosphatase increased, aspartate aminotransferase increased, and blood bilirubin increased) will not be summarized.

Confidential 49 of 52

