5.6.4.2 Nivolumab/IV Placebo

Nivolumab/IV placebo should be permanently discontinued for any of the following:

- Any Grade of GBS, MG and drug-related encephalitis and myelitis
- Any Grade 3 non-skin, drug-related AE lasting > 7 days or that recurs with any duration, with the following exceptions laboratory abnormalities, drug-related uveitis, pneumonitis, myocarditis, bronchospasm, neurologic toxicity, hypersensitivity reactions, infusion reactions, and endocrinopathies:
 - Grade 3 drug-related uveitis, pneumonitis, myocarditis, bronchospasm, neurologic toxicity, hypersensitivity reaction, or infusion reaction of any duration requires discontinuation
 - Grade 3 drug-related endocrinopathies, adequately controlled with only physiologic hormone replacement do not require discontinuation.
 - Grade 3 drug-related laboratory abnormalities do not require treatment discontinuation except:
 - Grade 3 drug-related thrombocytopenia >7 days or associated with bleeding requires discontinuation
 - AST, ALT, or total bilirubin elevations with AST or ALT > 5 × ULN or total bilirubin > 3 × ULN, regardless of baseline value, requires dose delay or discontinuation*
 - *In most cases of such AST or ALT elevation, IV study drug will be permanently discontinued. For participants with such AST or ALT elevations after the start of IV dosing, but on a background of previous elevations on the

first cycle of oral study drug, IV study drug hold is required, but discontinuation is not required, if AST/ALT elevations begin to resolve before the next scheduled infusion, and toxicity is considered to be mainly related to oral study treatment, after the investigator discusses the case with the study medical monitor. Levels will be monitored every 3 days; if they continue to rise more than 20%, the Hepatic Adverse Event Management Algorithm will be followed (see Appendix 7). Treatment with IV drug may be resumed if levels return to an ALT and ALT < 5 × ULN, and total bilirubin < 3 × ULN. If AST or ALT or total bilirubin elevations are considered mainly related to IV drug, and the investigator determines a possible favorable benefit/risk ratio that warrants continuation of study treatment, a discussion between the investigator and the Medical Monitor/designee must occur and approval from Medical Monitor prior to resuming therapy. IV drug dosing may resume when laboratory values return to baseline.

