9.7.2 Clinical Laboratory Evaluations

Clinical laboratory evaluations include the continuous variables for hematology, serum chemistry, and urinalysis. The laboratory values will be presented in SI units. The on-treatment period will be defined as the onset date on or after the date of first dose of study drug until 28 days after the last dose of oral study drug or 5 months after the last dose of IV study drug, whichever occurs later. Laboratory values collected during the on-treatment period will be included in the summary tables. The laboratory values collected after the on-treatment period will only be presented in the data listings.

The summary of laboratory data will include shift tables based on CTCAE for shifts in grade from baseline to maximum, minimum, and last value during the on-treatment period.

Supporting laboratory data including normal ranges and abnormal laboratory flags will be provided using by-patient listings. Separate listings will be produced for clinically significant laboratory abnormalities (ie, those that meet Grade 3 or 4 criteria according to CTCAE).

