#### 11.3 Clinical Laboratory Evaluations

This study uses a central laboratory assessment of all safety lab data. Local laboratory values that are clinically relevant will be added to the case report forms. All aggregate analyses of data will be done using only the central laboratory data, but the local laboratory data will be presented in patient level data listings.

Clinical laboratory evaluations include the continuous variables for hematology, serum chemistry, and urinalysis. The laboratory values will be presented in standard units. The ontreatment period with an onset date on or after the date of first dose of study medication until the date of the last oral study medication plus 28 days or date of last IV dose plus 5 months (ie, 152 days), whichever is the latest date. Laboratory values collected during the ontreatment period will be included in the summary tables. The laboratory values collected outside of the on-treatment period will only be presented in the data listings.

For visit-based summaries; the laboratory evaluations that are during the actual scheduled cycle visit (ie, EDC visit structure) will be used, otherwise, any unscheduled laboratory evaluations that are closest to and within the same actual scheduled cycle will be used. The data sets should highlight the value for the patient that was included in the summary table, wherever feasible. The summary tables and graphs will only display data if the number of observations is greater than 10 in each treatment arm.

The summary of laboratory data will include descriptive statistics of the maximum, minimum, and last value during the on-treatment period. Summaries using descriptive statistics of the change from baseline to the maximum, minimum, and last value during the on-treatment period will also be given.

Shifts from baseline to the maximum on-treatment toxicity grade (CTCAE Version 5.0 or later) for each lab parameter will be summarized.

Figures of the mean values over time with standard error bars will be presented for key safety laboratory parameters.

Confidential 42 of 52

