#### 11.2 Clinical Laboratory Evaluations

Clinical laboratory evaluations include the continuous variables for hematology, and serum chemistry. The laboratory values will be presented in standard units. Summary tables and graphical presentations will only include the laboratory values that are deemed to be "on-treatment" to oral study drug as follows: All clinical laboratory values with an onset date on or after the date of first dose of oral study medication until the date of the last oral study medication plus 28 days. The laboratory values collected outside of the on-treatment period for oral study drug will only be presented in the data listings.

For visit-based summaries; the laboratory evaluations that are during the actual scheduled cycle visit (ie, EDC visit structure) will be used, otherwise, any unscheduled laboratory evaluations that are closest to and within the same actual scheduled cycle will be used. The data sets should highlight the value for the patient that was included in the summary table, wherever feasible. The summary tables and graphs will only display data if the number of observations is greater than 10 in each treatment arm.

The summary of laboratory data will include descriptive statistics of the maximum, minimum, and last value during the on-treatment period. Summaries using descriptive statistics of the change from baseline to the maximum, minimum, and last value during the on-treatment period will also be given.

Shift summary tables from baseline to the maximum on-treatment toxicity grade (CTCAE v5.0 or later) for each lab parameter will be summarized.

Figures of the mean values over time with standard error bars will be presented for key safety laboratory parameters.

This study uses a central laboratory assessment of all safety laboratory data. Local laboratory values that are clinically relevant or support eligibility will be added to the CRFs. All aggregate analyses of data will primarily be done using only the central laboratory data. The local laboratory data will be presented in patient level data listings. However, an additional maximum on-treatment toxicity grade shift from baseline grade may be presented using both local and central laboratory data.

Additional detail regarding clinical laboratory evaluations are provided in Appendix 2.Urinalysis results will be reported in patient level listings.

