## 11.5 Examination of Safety in Subgroups

The following key safety output will be further explored within subgroups based on key intrinsic factors. The key identified safety output are:

- All TEAEs;
- Grade 3 or greater TEAEs;
- Serious TEAEs;
- TEAEs with an outcome of death;
- TEAEs leading to discontinuation of oral study drug;

- TEAEs leading to dose reduction of oral study drug;
- TEAEs resulting in interruption of oral study drug;
- TEAEs resulting in dose reduction or interruption of oral study drug; and
- Shift summary tables from baseline to the maximum on-treatment toxicity grade for each clinical laboratory parameter.

The following subgroups based on key intrinsic factors will be summarized:

- Age groups ( $< 65, 65-74, \ge 75; \ge 65$ ; and < 75 years old);
- Race (White, Other, and Unknown); and
- The stratification factor used for randomization of HRD classification (tBRCA, non-tBRCA LOHhigh, non-tBRCA LOHlow, and non-tBRCA LOHunknown) and the HRD Population.

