#### **Liver Function Tests**

Baseline results for four Liver Function Tests (LFTs); Alanine aminotransferase (ALT), Aspartate aminotransferase (AST), Alkaline phosphatase (ALP), and bilirubin will not receive a numeric grade (grade 1-5). They will be categorized in relation to the ULN (eg,  $\leq$  ULN, > ULN-3  $\times$  ULN, > 3  $\times$  ULN-5  $\times$  ULN). Shifts in grade from baseline to maximum on-treatment post-baseline for these events (ALT increased, ALP increased, AST increased, and blood bilirubin increased) will not be summarized.

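### Both SAPs drop the four liver tests from the promised grade-shift tables and plan no laboratory count of patients crossing the protocol's ULN thresholds

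*SAP*

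**What the plan says.** Four places promise shift tables, none with a liver exception:

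- Protocol 9.7.2: "The summary of laboratory data will include shift tables based on CTCAE for shifts in grade from baseline to maximum, minimum, and last value".
- COMBO SAP 11.3: "Shifts from baseline to the maximum on-treatment toxicity grade (CTCAE Version 5.0 or later) for each lab parameter will be summarized".
- MONO SAP 11.2: "Shift summary tables from baseline to the maximum on-treatment toxicity grade (CTCAE v5.0 or later) for each lab parameter will be summarized".
- MONO SAP 11.5, among the key safety outputs to be repeated in subgroups: "Shift summary tables from baseline to the maximum on-treatment toxicity grade for each clinical laboratory parameter".

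The laboratory appendices say otherwise. COMBO Appendix B (Liver Function Tests) states "Baseline results for four LTFs (ALT, AST, ALP and bilirubin) will not receive a numeric grade (grade 1-5", places those baselines in ULN categories instead, and adds that shifts in grade "for these events (alanine aminotransferase increased, alkaline phosphatase increased, aspartate aminotransferase increased, and blood bilirubin increased) will not be summarized". MONO Appendix 2 has the same exclusion: "ALT increased, ALP increased, AST increased, and blood bilirubin increased) will not be summarized". Neither appendix describes a shift by ULN category.

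The protocol sets its hepatic rules on the ULN scale. Section 5.6.4.2 acts on "AST or ALT > 5 × ULN or total bilirubin > 3 × ULN, regardless of baseline value". Sections 5.6.1.2 and 8.9 both use concurrent ALT or AST above 3 × ULN with total bilirubin above 2 × ULN, and 5.6.1.1.1 has an ALP criterion at 3 × ULN.

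**The concern.** A programmer cannot follow both the safety sections and the appendices, and the safety sections do not acknowledge the conflict. The liver tests are also the laboratory parameters where the table matters most. Protocol 1.2 says that ALT and AST elevations are common with rucaparib, and that with nivolumab they are not typical but can be an early sign of immune-mediated hepatitis. It gives clearer attribution between the two drugs as one reason for the oral-only first cycle.

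The comparison of Arm A with Arm B therefore needs a count, by arm, of patients whose values passed the levels at which the protocol itself acts. The question is whether any remaining laboratory output gives that count.

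**Working it through.** **What survives the exclusion**

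| Output | COMBO | MONO |
|---|---|---|
| Maximum, minimum and last value; change from baseline | 11.3 | 11.2 |
| Mean plots for key parameters | 11.3 | 11.2 |
| AE tables, with ALT/AST increased combined | 11.1 | 11.1 |
| Worst CTCAE grade, naming liver function | 11 | none |

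Continuous summaries and mean plots describe distributions; they do not count crossings. In MONO the shift tables are the only graded laboratory output named, so the exclusion leaves no promised graded summary of these tests. In COMBO the worst-grade summary is the only remaining candidate.

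**Can the worst grade be read back to the protocol's thresholds?**

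Inputs:
- The chemistry grading tables in both appendices. With a normal baseline, Grade 3 starts above 5 × ULN for ALT/AST and above 3 × ULN for bilirubin. With an abnormal baseline it starts above 5 × baseline and 3 × baseline.
- Protocol 4.2. ALT, AST and bilirubin may be up to 1.5 × ULN at entry, and bilirubin up to 2 × ULN with Gilbert's syndrome.

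Grade 3 cut in ULN units = multiplier × baseline:

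| Baseline (× ULN) | ALT/AST Grade 3 above | Bilirubin Grade 3 above |
|---|---|---|
| Normal | 5 | 3 |
| 1.1 | 5 × 1.1 = 5.5 | – |
| 1.25 | 5 × 1.25 = 6.25 | – |
| 1.5 | 5 × 1.5 = 7.5 | 3 × 1.5 = 4.5 |
| 2.0 (Gilbert's) | – | 3 × 2.0 = 6.0 |
| Protocol 5.6.4.2, any baseline | 5 | 3 |

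Examples at a baseline of 1.5 × ULN:
- ALT or AST of 6 × ULN is 6 / 1.5 = 4.0 × baseline, hence Grade 2, although it is above 5 × ULN.
- Bilirubin of 4.4 × ULN is 4.4 / 1.5 = 2.93 × baseline, hence Grade 2, although it is above 3 × ULN.

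**Normal baselines.** The 3 and 5 × ULN cuts for ALT/AST and the 1.5 and 3 × ULN cuts for bilirubin coincide with grade boundaries, so those crossings can be read from the grade. Two protocol cuts cannot. Bilirubin Grade 2 runs from 1.5 to 3 × ULN and so contains the 2 × ULN cut of 5.6.1.2 and 8.9. ALP Grade 2 runs from 2.5 to 5 × ULN and so contains the 3 × ULN cut of 5.6.1.1.1.

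**Concurrent criterion.** Grading each test separately cannot show whether ALT/AST above 3 × ULN and bilirubin above 2 × ULN occurred together. Neither SAP describes a count of that combination.

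**The case against.** The exclusion has a coherent reason. An abnormal-baseline grade is a multiple of that baseline, so the baseline cannot itself be graded in this way and a grade-to-grade shift is not well defined. MONO 11.2 also points to Appendix 2 for further laboratory detail, so there the text can be read as a general rule with an exception. This stands as a reason to change the scale of the table, but not to leave the table without a substitute. COMBO 11.3 has no such pointer.

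Threshold crossings are also partly captured as adverse events. Protocol 8.5 makes a laboratory abnormality an AE when it leads to action on study drug, needs intervention or is judged clinically significant. Section 5.6.4.2 requires delay or discontinuation of IV drug for drug-related elevations above its thresholds, and 8.9 requires potential drug-induced liver injury to be reported as an SAE. These events would reach the interruption, discontinuation and serious-event tables. That stands too, but these routes depend on attribution, clinical judgement or the absence of another apparent cause. They do not give a laboratory count.

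A reader might infer that only baseline-dependent grades are left for the liver tests, or that the worst-grade table can never show who crossed a threshold. The documents do not support either reading: continuous summaries, plots and AE tables remain, and with a normal baseline Grade 3 matches the 5 and 3 × ULN thresholds. Nor are these the only laboratory results left unsummarized. Both appendices send Cockcroft-Gault eGFR to listings, and MONO sends urinalysis to listings.

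Finally, protocol 9.7.2 commits to CTCAE shifts, not to a tabulation by ULN threshold. The ULN table is therefore a recommendation; the contradiction between sections is a defect of the text.

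**Conclusion.** The point holds in limited form. The safety sections and the appendices contradict each other in both SAPs, no replacement for the liver shifts is described, and no planned laboratory summary counts patients by arm who cross the protocol's ULN thresholds.

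At the 1.5 × ULN entry limit, the values graded below Grade 3 despite passing the 5.6.4.2 thresholds are those above 5 and up to 7.5 × ULN for ALT/AST, and above 3 and up to 4.5 × ULN for bilirubin. The gap narrows as baseline approaches ULN and vanishes for normal baselines, where only the 2 × ULN bilirubin and 3 × ULN ALP cuts stay hidden. How many patients this affects depends on the share with abnormal baselines, which the documents do not give.

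The arithmetic takes the entry limit as the largest baseline. The analysis baseline is the last value on or before the first oral dose, and may differ from the eligibility sample. Randomization should spread abnormal baselines similarly across arms, so this is a loss of information and not a claim of bias between arms. Efficacy and error control are untouched, and the importance is low.

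**What to change.** In COMBO Appendix B, replace the exclusion with a table, by arm, of baseline ULN category against worst on-treatment ULN category for ALT, AST, ALP and bilirubin. The cut-points should include 3 and 5 × ULN for ALT/AST; 1.5, 2 and 3 × ULN for bilirubin; and 3 × ULN for ALP. Add a count by arm of patients meeting the laboratory criteria of protocol 8.9 (ALT or AST above 3 × ULN with bilirubin above 2 × ULN), because separate tables per test cannot show it.

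State in 11.3 that grade shifts are not produced for these four tests and that the ULN table replaces them. State also whether the table uses central results only, as 11.3 says of aggregate analyses, or the stacked central and local results that Appendix B uses for grading.

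For MONO, use the same tables in any further safety output. Its primary analysis and the unblinding of Arms B and D are dated March 2022 in the COMBO SAP (2.3 and 3.5), so a change there cannot be presented as prespecified for that readout.

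The cost is a few extra safety tables and a few sentences. No new data are needed, and the baseline categories are already derived.
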